4. To describe the association of risk factors with performance on neurocognition, behavioral symptoms and MEPs amplitude measure of both groups at 15 treatment sessions (acute phase) and at 4 weeks of maintenance.

RESEARCH STRATEGIES OR METHODS

Methods:

According to the classification of: Alvan Feinstein, this is a clinical trial, single-blind, comparative study (CE + active tDCS vs CE + sham tDCS), randomized, longitudinal and prospective.

The sample size was calculated with the G*Power 3.1 program with an effect size of 0.03 with a formula for factorial ANOVA (between-subjects, within-subjects and interaction effect) with 90%

power, at an alpha of 0.05, with 2 groups and 3 measurements, the final sample would be constituted by a total of 60 participants, which means 30 patients in each analysis group (Jacob Cohen, 1977). The sample will be divided into 2 experimental groups of undergraduates.

1. Group EC + tDCS active = 30
2. Group EC + simulated tDCS =30

Study population:

Selection criteria

Inclusion criteria

1. Age \geq 18 years old.
2. Vaccinated against SARS-COV2 virus.
3. Students of the Faculty of Medicine of UNAM
4. Fluent in Spanish.
5. Adequate visual and auditory acuity to be able to perform neuropsychological tests and cognitive stimulation.
6. Depressive symptoms with working memory impairment (diagnosed by applying a specific neuropsychological battery).
7. That they are not under antidepressant pharmacological treatment prior to entering the investigation.
8. Good general health without medical illnesses (systemic arterial hypertension, diabetes mellitus, dyslipidemias, infections, thyroid disease, vitamin deficiencies) that do not interfere with the study.
9. Willingness to participate in a scheduled 8-week study and able to attend scheduled evaluations.

Exclusion criteria

1. Any neurological disease that allows suspicion of cognitive failure other than depression, such as Parkinson's disease, multiple infarct dementia, Huntington's disease, hydrocephalus, brain tumor, progressive supranuclear palsy, seizure disorder, subdural hematoma, multiple sclerosis, history of head injury with loss of alertness.
2. Participants with a history of severe psychiatric disorders according to DSM-5 (bipolar disorder, schizophrenia, chronic depression) or psychotic features, agitation or behavioral problems in the last three months that could lead to difficulties in complying with the protocol.

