Cognitive stimulation application

Cognitive stimulation will require a printed manual and will be carried out in groups of 13 participants, three sessions per week for three weeks (acute) and one session per week for four weeks (maintenance). In the following table, the domains to be stimulated are specified, selected from the U.M.A.N. manual.

DOMAINS	SPECIFIC DOMAINS
Orientation	Space Temporary Staff
Memory	Episodic Visual

	Long-term visual Semantics Visual recognition Job
Attention	Sustained Divided
Language	Expressive (oral) Printed (written) Fluency
Praxias	Constructive
Gnosias	Visual Space
Reasoning	Sequencing
Calculation	Mental
Processing speed	Written Visual

Definition of clinical and neuropsychological improvement or response to treatment.

A positive intervention effect will be considered if there is a change or remains the same in the following dimensions of the previously described instruments and scales

- Cognitive:** remain the same or increase by 1 point on the Montreal Cognitive Assessment.
- Behavioral:** no decrease in Lawton & Brody Index and Katz Index values, and 1-point decrease in Cummings Neuropsychiatric Inventory (NPI).
- Neuropsychological:** increase one standard deviation in T-score of the values obtained for each scale.
- Electrophysiological:** increase MEP amplitude from the seventh stimulus onwards * $p>0.05$
- Global:** remain the same or have increased 1 point on the Clinical Global Impression Scale and 1 on the Everyday Life Memory Failure Questionnaire.

General procedure

Students will be recruited through the dissemination of the study at the School of Medicine.

In all cases, they must comply with the safety measures to be able to participate and will be evaluated in an initial interview to ensure that they meet the inclusion criteria. In this interview they will be explained in detail what the study consists of, and if they agree to participate and sign the informed consent letter, a time will be agreed upon for the baseline clinical evaluation. Each of the candidates who meet the selection criteria will be verbally invited to participate in the study after explaining the objectives and procedures of the study.

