Prior to entry into this research project, the participant will have read and discussed the informed consent document with the principal investigator. Those who agree to participate will be asked to review and sign the informed consent form once all questions have been answered. All participants will be assigned a registration number. They will be given a booklet with information on cognitive stimulation and another on neuromodulatory techniques (rTMS and tDCS).

Subsequently, a clinical interview will be conducted to capture relevant demographic and clinical data, and the clinical and neuropsychological instruments will be applied for diagnostic certainty, which

in turn will count as baseline measurement. The total application of the instruments could be done in one session (3 hours with a 15-minute break). After that, the questionnaire of stimulation safety measures will be applied (see APPENDIX) and the recording of P300 potentials will be carried out with the application of the 5 Hz paradigm. The following measurements will be taken at the end of the 15 sessions and at the end of maintenance.

The patient will then be randomly assigned to one of the two tDCS groups and will be given 15 sessions, 5 per week from Monday to Friday and then one per week for 4 weeks. After each session, adverse effects will be asked about and recorded in a questionnaire (see APPENDIX). They will be evaluated at the beginning, at the end of the 15 sessions (three weeks) and four weeks after the end of the study maneuver (the characteristics of each maneuver are described in the methods section corresponding to each stimulation technique). At the same time, all participants will receive three sessions per week of cognitive stimulation using the manual adapted to Mexican Spanish of the UMAM method.

The randomization will be carried out with a list of numbers in Excel that will be in charge of one of the members of the research who will not have contact with the participants.

The applicators of the stimulation techniques will be the same as the assessors and will not remain blind to the maneuver, unlike the students. All applicators will be randomized to form the two groups and the applicator of the techniques will know whether it is the experimental maneuver or the placebo maneuver.

Statistical analysis

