A descriptive analysis of the demographic and clinical characteristics will be performed with frequencies and percentages for the categorical variables and with means and standard deviations for the dimensional variables. Repeated measures ANOVA will be used for the dimensional variables under study. The level of statistical significance was set at a $p \leq 0.05$ for all analyses. Clinical, demographic and baseline variables will be tested for differences between groups with χ^2 or analysis of variance (ANOVA). If any differences between groups emerged ($p < 0.05$), the corresponding variables will be included as covariates in the following analyses.

The groups will be included in a two-measure repeated multivariate analysis of variance (MANOVA) model to examine the direction of changes (time effect) between groups (interaction effect) in terms of the variables to be studied, including cognition, working memory and P300 potentials. A p value of 0.05 will be used as statistically significant for the MANOVA analyses due to the objective of testing the therapeutic efficacy of the intervention.

tDCS+EC reduce Type I error.

Effect sizes of comparisons were estimated using partial eta squared (η^2) and reference values for interpretation of 0.01 = small, 0.06 = medium, 0.14 = large (COHEN, 1988).

All these analyses will be performed using the Statistical Package for the Social Sciences (SPSS), version 22.

ETHICAL CONSIDERATIONS AND/OR LETTER OF INFORMED CONSENT

This project offers a form of therapeutic intervention both by the application of tDCS and the application of the paradigm with TMS, which correspond to a level of risk higher than the minimum according to the regulation of the general health law on research for health, article 17: those in which the probabilities of affecting the subject are significant, among which radiological studies with microwaves and drug trials are considered, due to the fact that brain stimulation interventions approved by the health authorities (e.g. Food and Drug Administration of the USA and COFEPRIS) are carried out for their use in major depression.

The study was planned in accordance with the principles stipulated in the Declaration of Helsinki. The data generated from the research will be used only for scientific purposes without any other use, thus guaranteeing absolute confidentiality of the data obtained from the participants (WMA Declaration of Helsinki, 2013).

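### Scores that qualify a student as impaired also serve as baseline, so the time effect and any single-arm response rate can show improvement without a treatment effect; the plan should rest efficacy on the active-versus-sham contrast alone

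*Combined protocol and SAP*

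**What the plan says.** Inclusion criterion 6 reads "Depressive symptoms with working memory impairment (diagnosed by applying a specific neuropsychological battery". No test or cut-off is named.

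General procedure describes one pre-treatment application of the neuropsychological tests. There "the clinical and neuropsychological instruments will be applied for diagnostic certainty", and this "in turn will count as baseline measurement". It adds that "The total application of the instruments could be done in one session". Randomization comes afterwards. On follow-up: "The following measurements will be taken at the end of the 15 sessions and at the end of maintenance". No run-in, repeat screening or second baseline is described.

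The section defining improvement or response to treatment opens: "A positive intervention effect will be considered if there is a change or remains the same". Its neuropsychological criterion is "increase one standard deviation in T-score of the values obtained for each scale". Sham is not mentioned in that section.

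Statistical analysis includes the groups in a repeated-measures model "to examine the direction of changes (time effect) between groups (interaction effect". It sets 0.05 for that model and gives testing of therapeutic efficacy as the reason. It does not say which of the two effects counts as evidence.

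**The concern.** A student selected for a low score has, on average, a score that is low partly through measurement error on that day. At the next sitting the error is drawn afresh and the score moves back towards the student's own level. This is regression to the mean, and it needs no treatment. It acts in both arms, and the plan uses two quantities that absorb it.

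- The **time effect** pools the rise over both arms. It also contains practice on repeated tests and the effect of the cognitive stimulation that everyone receives.
- The **1 SD response rule** compares each student with his or her own qualifying score and labels the result an intervention effect.

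At stake is what the trial may conclude. On the present wording, a significant time effect or a count of responders in the active arm could be reported as benefit of tDCS when the sham arm shows the same.

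**Working it through.** The plan gives no figure on this point, so there is none to reproduce.

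**Inputs from the documents:** one qualifying sitting used as baseline; response at a rise of 1 SD (10 T-score points); 30 students per arm; three measurements; alpha 0.05.

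**Assumed inputs (not in the documents):** a single qualifying test with a hard cut-off c of -1 or -1.5 SD; retest correlation r of 0.5 to 0.9; applicants distributed like the norm population; no true change.

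**1. Mean qualifying score.** For a standard normal score below c, the mean is -φ(c)/Φ(c).
- c = -1: -0.2420/0.1587 = -1.525 SD
- c = -1.5: -0.1295/0.0668 = -1.939 SD

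**2. Expected rise with no effect** = (1 - r) × |mean|.
- Smallest: (1 - 0.9) × 1.525 = 0.15 SD
- Middle: (1 - 0.7) × 1.525 = 0.46 SD
- Largest: (1 - 0.5) × 1.939 = 0.97 SD

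**3. Share rising 1 SD or more by chance.** Given baseline x, the probability is 1 - Φ[(1 + (1 - r)x)/√(1 - r²)], averaged over x below c. Without selection it is 1 - Φ[1/√(2(1 - r))].

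| r | c = -1 | c = -1.5 | unselected |
|---|---|---|---|
| 0.5 | 39% | 49% | 16% |
| 0.7 | 23% | 28% | 10% |
| 0.9 | 3% | 3% | 1% |

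At c = -1 and r = 0.7 this is 30 × 0.23, or about 7 chance responders in each arm.

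**4. The tests.** Trials with no true change and no treatment effect were simulated (1,500 per setting, 30 per arm, three measurements, repeated-measures ANOVA at 0.05, c = -1 and -1.5, r = 0.6 to 0.9). The time effect was significant in 80% to 100% of trials. The group-by-time interaction was significant in 4% to 6%, so it keeps its level.

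**5. Sensitivity to who applies.** Scores regress to the applicants' own mean. With c = -1 and r = 0.7, an applicant mean of -0.5 SD gives a rise of 0.34 SD and 18% chance responders. A mean of -1 SD gives 0.24 SD and 15%.

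**6. Effect on the comparison of response rates.** With c = -1, r = 0.7 and an assumed true effect of 0.5 SD:

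| Baseline | Active | Sham | Difference | Ratio |
|---|---|---|---|---|
| Qualifying score | 48% | 23% | 25 points | 2.1 |
| Separate later score | 26% | 10% | 16 points | 2.6 |

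In all 18 combinations tried (two cut-offs, r = 0.5, 0.7, 0.9, effects 0.3, 0.5, 0.8 SD) the absolute difference was larger with the qualifying score as baseline, and the ratio was smaller.

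**The case against.** The strongest reply is that the trial's question is untouched. The research question, hypothesis and general objective all compare active with sham, and students are randomized after the baseline, so both arms regress alike. Statistical analysis specifies no within-arm test and never takes up the 1 SD rule. On this view, the concern only predicts misreporting. Moreover, the time effect could not isolate tDCS in any case, because both arms receive cognitive stimulation and repeat the tests.

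Most of this stands. A reader might infer that the main comparison is biased; randomization after baseline and the 4% to 6% interaction error rate rule that out. The reply does not dispose of the response definition, however, which declares a positive intervention effect from within-participant change alone. Nor does it settle the 0.05 test, which is tied to therapeutic efficacy without saying that only the interaction counts. That the time effect is uninterpretable for tDCS on other grounds is a further reason to say so in the plan.

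The objection to the size also stands in part. The protocol speaks of a battery, names no cut-off, and depressed students may truly average below the norm. The figures are a range under assumptions, and at r = 0.9 the effect is small.

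**Conclusion.** The point holds for the time effect and for any response rate read from one arm; it does not hold for the randomized contrast. Under the assumed inputs, the rise with no treatment effect is 0.15 to 0.97 SD, and 3% to 49% of students reach the 1 SD threshold by chance, against 1% to 16% without selection. Both are smaller if applicants truly average below the norm. The effect is weaker for scales not used for selection, such as P300.

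Two further inferences are tempting and are not supported. The first is that chance responders dilute a true difference in response. They raise the rate in both arms and shrink the ratio, but the absolute difference grew in every setting examined. The second is that the baseline must be measured again, or the qualifying test left out of the response rule. A new baseline would shrink the absolute contrast in response. The only equivalent forms the protocol mentions are for a verbal memory test, whereas entry rests on working memory. Leaving out the qualifying test could remove working memory, a principal outcome, from the rule.

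**What to change.** Two changes of wording.

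1. **Statistical analysis.** State that only the group-by-time contrast (active minus sham in change from baseline) is evidence of efficacy, and that the time effect and any within-arm p-values are descriptive.
2. **Definition of improvement or response.** State that the 1 SD response is reported as a proportion in each arm, and that a positive intervention effect is concluded only from the active-versus-sham difference in those proportions.

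Neither change needs an extra visit, test or participant. The cost is that a rise seen in both arms, or a responder count in the active arm alone, can no longer be presented as an effect of tDCS.

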Aims: To evaluate the effect of active CE + tDCS in CPFdl to improve scores on working memory tests, cognitive functioning, P300 cognitive evoked potentials and academic performance in medical students with depressive symptomatology vs simulated CE+ tDCS.

Materials and Methods: This is a single-blind, comparative (cognitive stimulation + active tDCS vs. cognitive stimulation + simulated tDCS), randomized, longitudinal and prospective clinical trial. Analysis: A descriptive analysis of demographic and clinical characteristics will be performed with frequencies and percentages for categorical variables and with means and standard deviations for dimensional variables. Mean comparison tests (t-tests), analysis of variance (ANOVA) and correlation tests. Significance level $p \leq 0.05$.

THEORETICAL FRAMEWORK

Transcranial direct current stimulation is a method of brain stimulation that involves passing a current (1 to 2 mA) through the cortex using at least two electrodes. Transcranial direct current stimulation (tDCS) is one of the most studied techniques in noninvasive neuromodulation. With a very good safety profile and low cost, it has been widely used to modulate cognition and behavior in both experimental and clinical settings (Coffman et al., 2014; Fregni et al., 2021; Guidetti et al., 2021). A growing body of literature, including randomized controlled trials, reports clinical benefits of tDCS for many psychiatric symptoms, such as depression, anxiety, psychosis, addiction, and cognitive functions (Dedoncker et al., 2016; Huang et al., 2021; Sagliano et al., 2019; Yamada et al., 2021). However, only a few studies have investigated the brain mechanism underlying the effects of tDCS on cognitive processing, especially through electrophysiological markers, such as P3 (Mendes et al., 2021). tDCS has considerable potential as a treatment because of its relative cost, portability, safety, and ease of use compared to other neuromodulation methods. Early studies evaluated the effects of tDCS on the motor cortex; however, more recent research has also focused on its effects on the dorsolateral prefrontal cortex (dorsolateral prefrontal cortex (DLPFC), particularly for treating psychiatric disorders and modulating cognitive performance.

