Major depressive disorder (MDD) is a major public health problem, adversely affecting cognition, with cognitive deficits affecting information processing speed, attention, memory, executive function, and working memory. In addition, cognitive deficits associated with MDD do not resolve after successful treatment of depressive symptoms. In one study, 94% of individuals with MDD and cognitive deficits at the start of treatment retained these deficits one year later, despite achieving clinical remission. Long-term maintenance of antidepressants does not prevent cognition decline, despite maintaining recovery from depression (Brunoni and Vanderhasselt, 2014; Ke et al., 2019; Mancuso et al., 2016). The present study aimed to evaluate the effectiveness of multi-session dorsolateral prefrontal cortex stimulation (in conjunction with cognitive stimulation) on working memory and academic performance in medical school students subjected to significant stressors and with a high prevalence of depression. Similar to single-session working memory enhancement studies, the anode will be placed over the dorsolateral prefrontal cortex and the cathode over the orbitofrontal prefrontal cortex (contralateral above the right eye).

HYPOTHESIS

CE + tDCS will be more effective compared to CE + tDCS-placebo or sham in improving scores on tests of working memory, cognitive functioning, P300 cognitive potentials, and academic performance in UNAM medical students with depressive symptoms at 15 treatment sessions (acute phase) and at 4 weeks of maintenance.

OBJECTIVES

To evaluate the effect of CE + tDCS to improve scores on working memory tests, cognitive functioning, P300 cognitive evoked potentials and academic performance in UNAM medical students with depressive symptoms vs simulated CE+ tDCS.

Specific objectives

1. To compare the presence of adverse effects and tolerability of both groups (EC+tDCS and EC+ tDCS- placebo or sham) at 15 treatment sessions (acute phase) and at 4 weeks of maintenance.
2. To describe the association of MEPs amplitude with performance on neurocognition and behavioral symptoms of both groups at 15 treatment sessions (acute phase) and at 4 weeks of maintenance.
3. To describe the association of P300 cognitive evoked potentials with performance in neurocognition and behavioral symptoms of both groups at 15 treatment sessions (acute phase) and at 4 weeks of maintenance.

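### Four unranked outcome domains at two follow-up visits are each tested at 0.05, and no legible text gives a primary outcome, a primary visit, a test order or an any-or-all rule for success.

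*Combined protocol and SAP*

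**What the plan says.** The Hypothesis section expects active stimulation to be superior "in improving scores on tests of working memory, cognitive functioning, P300 cognitive potentials, and academic performance", and it places that benefit "at 15 treatment sessions (acute phase) and at 4 weeks of maintenance". That makes four domains and two post-baseline visits, none of them marked as primary.

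The Statistical analysis section sets a 0.05 significance level for every analysis and describes two families of test:

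- Univariate: "Repeated measures ANOVA will be used for the dimensional variables under study".
- Multivariate: "The groups will be included in a two-measure repeated multivariate analysis of variance (MANOVA) model". The variables given as examples are cognition, working memory and P300. Academic performance is not among those named.

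The level for the second family is justified by its purpose: "A p value of 0.05 will be used as statistically significant for the MANOVA analyses due to the objective of testing the therapeutic efficacy". A short line on Type I error follows, but it is incomplete as read.

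The sample size was computed "with 2 groups and 3 measurements". The General procedure likewise plans assessments at baseline, after the 15 sessions and at the end of maintenance. The summary's Materials and Methods paragraph lists the methods more loosely: "Mean comparison tests (t-tests), analysis of variance (ANOVA) and correlation tests".

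**The concern.** The hypothesis is confirmatory in tone, and the 0.05 level is justified by the aim of testing efficacy. For a confirmatory claim, a reader needs to know in advance which score, visit and test decide the question, and how the four domains combine. The legible text leaves all of these open.

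The section that defines response to treatment does not fill the gap. It lists five dimensions without ranking them and does not say whether one or all must be met. It states no comparison between groups, names no working-memory score, and mentions neither P300 nor academic performance.

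At stake is how a mixed result is reported. With one nominally significant domain out of four, the plan would not stop the authors from presenting it as support for the hypothesis, or a critic from calling the hypothesis unsupported. Neither could be refuted from the document.

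**Working it through.** **Inputs from the document.** Level 0.05 per test (Statistical analysis); four domains and two follow-up visits (Hypothesis); 30 per group, 2 groups, 3 measurements (Methods, sample size).

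**Inputs assumed.** Each domain is represented by one test. The correlation between domains is r = 0 to 0.9, because the document gives none.

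**Step 1: the plan's own level.** A single group-by-time F test has 3 − 1 = 2 and (60 − 2) × (3 − 1) = 116 degrees of freedom. Simulated with no effect and sphericity assumed, it rejects in 4.9% to 5.1% of trials. The stated 5% therefore holds for one test.

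**Step 2: any one of four, independent.** 1 − (1 − 0.05)^4 = 1 − 0.8145 = 0.1855, from the unrounded value 0.18549, i.e. 18.5%.

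**Step 3: any one of four, correlated.** For equicorrelated normal test statistics with c = 1.96, the chance of at least one rejection is 1 − ∫ [Φ((c − √r·x)/√(1 − r)) − Φ((−c − √r·x)/√(1 − r))]^4 φ(x) dx. The planned F test was also simulated (150,000 trials per value of r).

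| r | Normal tests | Group-by-time F tests |
|---|---|---|
| 0 | 18.5% | 18.6% |
| 0.3 | 17.4% | 17.5% |
| 0.5 | 15.6% | 16.0% |
| 0.7 | 13.0% | 13.3% |
| 0.9 | 9.4% | 9.7% |

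**Step 4: all four required.** The chance that all four reject cannot exceed the chance that any one true null rejects, which is 0.05. The error is at most 5% at any correlation.

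**Step 5: sensitivity to the count.** Three domains, as named for the MANOVA: 1 − 0.95^3 = 14.3%. Four domains at two visits tested separately: 1 − 0.95^8 = 33.7%. Both assume independence.

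**Step 6: candidate procedures.**

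- Holm over four: the smallest p must be at most 0.05/4 = 0.0125. With no effects and independence, the error is 1 − (1 − 0.0125)^4 = 4.9%, and it is at most 5% at any correlation.
- One primary at 0.05, then Holm over three (first threshold 0.05/3 = 0.0167): simulated error is 5.0% when nothing has an effect. When only the primary has a true effect, the error over the three secondaries is 3.0% to 4.9%.

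**Step 7: what 30 per group can detect.** Two-sample t-test on change from baseline, 58 degrees of freedom, noncentrality d × √(30/2), all 30 analysed, d in SDs of the change score.

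| Two-sided level | 80% power | 90% power |
|---|---|---|
| 0.05 | 0.74 | 0.85 |
| 0.0167 | 0.86 | 0.97 |
| 0.0125 | 0.89 | 1.00 |

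**The case against.** The strongest reply is that the 18.5% belongs to a rule the plan never states. The hypothesis joins its domains with *and*. Read literally, that requires all four, and Step 4 then caps the error at 5%. This stands. A reader might infer that the trial as planned has an 18.5% false-positive rate, and the documents do not support that. They support only that the rule is not given, so the figure is an illustration.

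A second reply is that the MANOVA is the efficacy test, and one omnibus test at 0.05 holds the error at 5% when no outcome has an effect. That would be a sound gatekeeper if the ANOVAs depended on it. The legible text does not make them depend on it, and academic performance is not among the variables named. The Type I error line may once have explained the intent. Because it is incomplete as read, it is not counted as an error, and a reader should not conclude that the authors had no multiplicity rule in mind.

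Third, the count of four is itself a choice, and Step 5 shows how far the figure moves with it.

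Two further inferences should be resisted. The t-tests appear only in the summary, with no variables attached, so they are not shown to be rival efficacy tests. A background remark links working memory to the evoked-potential waveform, but the hypothesis and the analysis section list working memory and P300 separately. It does not show that one could stand in for the other.

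**Conclusion.** The concern holds as a gap in the decision rule. All outcomes are tested at 0.05, four domains and two visits are hypothesised without ranking, and no legible text gives a primary outcome, a primary visit, a test order, a dependence of the ANOVAs on the MANOVA, or an any-or-all criterion. Depending on which unstated rule is applied, the error for the overall claim ranges from at most 5% (all four required) to 18.5% (any one of four, independent), with about 17% to 9% at assumed correlations of 0.3 to 0.9. The upper figures rest on the any-one rule, one test per domain and assumed correlations, none of which the document states. The absence of a rule does not depend on those assumptions.

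**What to change.** Amend the Statistical analysis section before any outcome data are seen.

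1. Name one measure for each hypothesised domain, including academic performance, for which the methods describe no measure. Name one visit for the confirmatory group-by-time contrast, taken from the planned three-measurement repeated-measures model.
2. Control the error across domains in one of two ways:
   - Holm over the four domains; or
   - one primary measure at two-sided 0.05 and, only if it is significant, Holm over the other three. The choice is the team's. Working memory is the natural candidate, because it comes first in the hypothesis and its impairment is an entry requirement: "Depressive symptoms with working memory impairment (diagnosed by applying a specific neuropsychological battery".
3. State the role of the MANOVA and what two-measure means there, given the three planned assessments. If it means two visits, say which. Restore the full text of the Type I error line.
4. Label all remaining measures, visits and tests exploratory.
5. Restate the power statement for the chosen contrast.

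No new visit is needed, since both follow-ups are already scheduled. The costs are a stricter threshold for some domains (smallest p at most 0.0125 under Holm over four, or 0.0167 for the secondaries) and less confirmatory weight for outcomes or visits not named. The factorial-ANOVA sample-size basis would also no longer match the main test. With all 30 per group analysed, the contrast at two-sided 0.05 detects 0.74 SD of change with 80% power and 0.85 SD with 90%. The elimination criteria suggest that fewer may be available, which would raise both figures.

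### Uncorrected partial eta squared with fixed small/medium/large marks and no signed difference or interval: with 60 participants the small mark, and in the MANOVA the medium mark, is often passed by chance

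*Combined protocol and SAP*

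**What the plan says.** The Statistical analysis section of the combined protocol and SAP states: "Effect sizes of comparisons were estimated using partial eta squared". It then gives "reference values for interpretation of 0.01 = small, 0.06 = medium, 0.14 = large". The index is not bias-corrected, no interval accompanies it, and nothing restricts the labels to significant results.

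Two models are named. One is a repeated measures ANOVA for each continuous variable. The other is introduced as follows: "The groups will be included in a two-measure repeated multivariate analysis of variance (MANOVA) model". It covers cognition, working memory and P300, but the number of dependent variables is not given. The section sets p ≤ 0.05 for all analyses and names 0.05 again for the MANOVA as the test of efficacy.

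The sample size paragraph under Research strategies or methods is written "with 2 groups and 3 measurements" and concludes that "the final sample would be constituted by a total of 60 participants", "which means 30 patients in each analysis group".

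The Hypothesis is directional: "CE + tDCS will be more effective compared to CE + tDCS-placebo or sham".

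**The concern.** Sample partial eta squared is never negative, so chance variation alone pushes it above zero. In a small trial its average under no effect can exceed the lowest mark, and in a multivariate test that average rises with the number of variables tested together. Fixed marks ignore both facts. A word such as small or medium may then describe noise, and no planned interval would show this.

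The index also has no sign. Sham beating active by some amount gives the same value and label as active beating sham. The planned effect size therefore cannot answer the directional question in the Hypothesis. At stake is how the size of the result is described, not the error rate of the significance tests.

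**Working it through.** **The plan's own figure.** The plan gives no figure for how the index behaves. The only plan figure used is the total of 60. That total is not reproduced from the stated inputs. If the planning value in "with an effect size of 0.03 with a formula for factorial ANOVA" is Cohen's f, the three-measurement interaction needs about 2,346 participants at an assumed within-person correlation of 0.5 (472 at 0.9; 4,690 at 0). That is a separate matter. The results below depend on 60 participants in two groups of 30, not on how 60 was reached.

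**Formula.** With no effect, partial eta squared = df1·F/(df1·F + df2), which follows Beta(df1/2, df2/2) with mean df1/(df1 + df2).

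**Degrees of freedom.** The error degrees of freedom are 60 − 2 = 58.
- One outcome, two visits: 1 and 58.
- One outcome, three visits, univariate interaction under sphericity: 2 and 2 × 58 = 116.
- One outcome, three visits, multivariate form: 2 and 57.
- Two-visit MANOVA of p variables, group-by-time: p and 59 − p, so the mean under no effect is p/59.

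The word two-measure could mean two visits or two dependent variables, and the sample size paragraph has three measurements, so these versions were all computed.

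**Two cases by hand.** For df 2 and 116 the chance of exceeding x is (1 − x)^58, so 0.99^58 = 0.558 and 0.94^58 = 0.028. For df 2 and 57 it is (1 − x)^28.5, so 0.94^28.5 = 0.17.

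**Results under no effect, 60 participants.**

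| Test | df | Mean | Reaches 0.01 | Reaches 0.06 | Reaches 0.14 | Value at p = 0.05 |
|---|---|---|---|---|---|---|
| One outcome, two visits | 1, 58 | 0.017 | 44.7% | 5.9% | 0.3% | 0.065 |
| One outcome, three visits, univariate | 2, 116 | 0.017 | 55.8% | 2.8% | 0.02% | 0.050 |
| One outcome, three visits, multivariate; or MANOVA, 2 variables | 2, 57 | 0.034 | 75.1% | 17.2% | 1.4% | 0.100 |
| MANOVA, 3 variables | 3, 56 | 0.051 | 90.4% | 32.1% | 3.6% | 0.129 |
| MANOVA, 4 variables (assumed) | 4, 55 | 0.068 | 96.7% | 48.3% | 7.7% | 0.156 |
| MANOVA, 6 variables (assumed) | 6, 53 | 0.102 | 99.7% | 75.7% | 21.8% | 0.205 |

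A simulation of 20,000 trials for df 1 and 58 gave 44.7%, 5.6% and 0.3%, in agreement with the first row.

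**Non-significant but labelled.** Where a mark lies below the value at p = 0.05, the 5% of significant results can be subtracted.
- One outcome: 40% (two visits) or 51% (three visits, univariate) of tests under no effect are non-significant yet at least small. Non-significant medium occurs in 0.9% with two visits and cannot occur in the three-visit univariate test. Non-significant large cannot occur in either.
- MANOVA of three variables: 27% are non-significant yet at least medium. Non-significant large cannot occur, because 0.129 is below 0.14.
- MANOVA of four variables: 2.7% are non-significant yet large. With six it is 17%.

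**The other side of the same problem.** From four variables upwards the value at p = 0.05 exceeds 0.14, so a significant omnibus MANOVA result can only be labelled large.

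**What an interval or correction would show.** For df 1 and 58, an observed 0.06 has p = 0.059 and a 95% interval of about 0.00 to 0.20. Its bias-adjusted value is 1 − 0.94 × 59/58 = 0.044. An observed 0.01 adjusts to 1 − 0.99 × 59/58 = −0.007, which is below zero.

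**The case against.** The strongest reply is that the labels are an addition. The plan keeps p ≤ 0.05 as its criterion and names the MANOVA at 0.05 as the efficacy test, and nothing says that a non-significant result will be declared an effect. This stands. A reader might infer that results of an ineffective treatment will be reported as small, medium or large effects. The documents do not support that: they leave it possible, but do not plan it.

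Second, the three marks do not fail alike. For a single outcome, chance medium is about as frequent as a false-positive test, and large is very rare. This also stands.

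Third, the most striking figures need a variable count that the plan does not give. Six is plausible: Instruments or tools lists four tests, and P300 latency and amplitude would make six. It remains an assumption. The statement that significant results must be labelled large likewise applies only to the omnibus MANOVA with at least four variables, because significant single-outcome results start at 0.050 to 0.065.

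Fourth, direction is not absent from the plan. The summary mentions t-tests, the MANOVA is meant to show the direction of change, and the definition of improvement uses directions and scale units. None of these is a planned estimate of the treatment difference with an interval, so they do not fill the gap.

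Finally, one might object that the MANOVA mixes scores where higher is better with P300 latency, where lower is better. This is not a separate fault: reversing a variable leaves the statistic unchanged. It only restates the lack of a sign.

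**Conclusion.** The concern holds in a limited form. At 60 participants the small label is uninformative for single outcomes, since it is reached by chance 45% to 56% of the time (75% if the multivariate form of the three-visit test is read). The medium label is unreliable in the MANOVA: 17% with two variables and 32% with three. Chance large labels become material only with more variables than the three domains named (22% with an assumed six). Whatever the count, the index cannot show which arm did better, and no signed estimate or interval is planned to supply this. The significance tests and their error rate are untouched.

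The figures assume no dropout (losses would raise the chance rates), sphericity for the three-visit univariate test, and the usual normal-theory conditions.

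**What to change.** Replace the effect-size sentence in Statistical analysis with: *For each outcome, the effect size is the active-minus-sham difference in baseline-adjusted means, with its 95% confidence interval, in test units and in SD units, after the 15 sessions and at the end of maintenance.* Delete the three reference values. If a variance-explained index is kept, use a bias-corrected one such as omega squared, without labels.

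The change needs no new data and no more participants. It adds one baseline-adjusted model per outcome; this is a real addition, because the plan now adjusts only for variables that differ between groups at baseline. The stated effect sizes will also look smaller.
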